### **Product Preference/Acceptability Assessment**

A product preference/acceptability questionnaire will be administered by CASI to participants at the Enrollment Visit and Visit 6 (Day 28), with a more thorough questionnaire administered at Visit 9 (PUEV/Early Termination Visit). HIV prevention product preference will also be assessed at the PUEV/Early Termination Visit. This questionnaire includes structured questions about the participant's attitude related to the IVR (product characteristics; likes and dislikes concerning the IVR), her experiences using the IVR (e.g., genitourinary discomfort, ease of use/removal, displacement, willingness to use during menstruation, willingness to use in the future), effect on sex, and partner's reactions. Measures used previously in MTN-036 and other microbicide trials will be employed.

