#### **10.4.2 Secondary Endpoints**

Adherence will be measured by the percentage of participants who keep the IVR inserted at all times in the vagina over the course of 91 days. (Clinician-initiated VR removals for the purpose of clinical examination will be excluded from consideration.) A sample size of 48 participants will provide a precision of 13.0% (i.e., half the width of the 95% confidence interval) assuming an observed adherence of 75%.

Overall acceptability will be measured by the degree (on a scale of 1 to 10) to which participants like or dislike using the IVR over the course of 91 days. Previous studies using such a scale indicate that the standard deviation of this score is approximately 2.4. Assuming a similar standard deviation and 32 participants in the active IVR arm and 16 in the placebo arm, the study will have 90% power to detect a difference in the acceptability score of 2.65.

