## APPENDIX I: SCHEDULE OF STUDY VISITS AND EVALUATIONS

	Visit 1 SCR	Visit 2 ENR (Day 0)	Visit 3, 4 (Days 1, 7)	Visit 5 (Day 14)	Visit 6 (Day 28)	Visit 7 (Day 42)	Visit 8 (Day 56)	Visit 9 PUEV/Early Termination (Day 91)	Visit 10 Final Contact (Day 92)
ADMINISTRATIVE AND REGULATORY									
Obtain written informed consent(s)	X								
Assign a unique Participant Identification (PTID) number	X								
Assess and/or confirm eligibility	X	X							
Collect demographic and background information	X								
Collect/review/update locator information	X	X	X	X	X	X	X	X	X
Randomization to product and biopsy schedule		X							
Provide reimbursement	X	X	X	X	X	X	X	X	X
Schedule next visit/contact	*	*	X	X	X	X	X	X	*
BEHAVIORAL/COUNSELING									
HIV pre- and post-test counseling	X	X	*	*	*	*	*	X	*
HIV/STI risk reduction counseling	X	X	*	*	*	*	*	X	*
Protocol counseling	X	X	X	X	X	X	X	X	
Collect product use information					X		X	X	
Collect product preference/acceptability information		X			X			X	
Behavioral assessment		X			X		X	X	
In-depth interview (IDI)								X♦ (subset)	
CLINICAL									
Collect medical eligibility information (including exclusionary conditions and medications)	X	X							
Collect/review/update medical/menstrual history	X	X	X	X	X	X	X	X	X
Collect/review/update concomitant medications	X	X	X	X	X	X	X	X	X
Perform physical exam (Targeted at Visits 2-10)	X	X	*	*	*	*	*	*	*
Perform pelvic exam	X	X	X	X	X	X	X	X	*
Treat or prescribe treatment for RTI/UTI/STIs	*	*	*	*	*	*	*	*	*
Digital exam by clinician to check IVR placement		X							
Provide available test results	X	X	X	X	X	X	X	X	X
Collect AEs			X	X	X	X	X	X	X

		Visit 1 SCR	Visit 2 ENR (Day 0)	Visit 3, 4 (Days 1, 7)	Visit 5 (Day 14)	Visit 6 (Day 28)	Visit 7 (Day 42)	Visit 8 (Day 56)	Visit 9 PUEV/Early Termination (Day 91)	Visit 10 Final Contact (Day 92)
LABORATORY										
URINE	Pregnancy test	X π	X π	*	*	X π	*	X π	X π	*
	Urine dipstick/culture	*	*	*	*	*	*	*	*	*
BLOOD	HIV-1/2 testing	X	X	*	*	*	*	*	X	
	Plasma for archive		X							
	AST/ALT	X				*	*	*	X	
	CBC with differential and platelets	X	*	*	*	*	*	*	X	*
	Serum creatinine	X	*	*	*	*	*	*	X	*
	Hep B surface antigen	X								
	Syphilis serology	X		*	*	*	*	*	*	
	HSV 1/2 serology		X							
	TFV levels			X	X	X		X	X∞	X
PELVIC	NAAT for GC/CT and trichomonas	X	*	*	*	*	*	*	*	
	Saline/KOH wet mount with pH for candidiasis and/or BV	*	*	*	*	*	*	*	*	*
	Pap test	X^								
	Vaginal swabs for microbiota		X			X		X	X	
	Vaginal Gram stain		X			X		X	X	

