3. GENERAL DATA ANALYSIS CONSIDERATIONS

3.1 Analysis Set(s)

For the primary PK endpoint, all participants with concentration results from at least two sample collection timepoints will be included in the PK analysis set. For the primary safety endpoint and secondary

adherence endpoint, all participants with a study IVR inserted at any time during the trial will be included in the analysis set. For the secondary acceptability endpoint, all participants who completed question J2 of the product use end visit computer assisted self-interview (PUEV CASI) behavioral questionnaire will be included in the analysis set.

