9.2 Acceptability Secondary Endpoint

To assess acceptability of the study IVR, the participants' answers to questions J2 ("Overall, how much do you like the ring?"), based on the participants' self-report by CASI at the Product Use End Visit (PUEV) or Early Termination Visit, will be used for this the primary endpoint analysis. The acceptability response is on the 10-point Likert scale and will be summarized by calculating the mean, standard deviation, median, IQR, minimum, and maximum values and 95% CI overall, and by study arm. A bar plot of scores reported for question J2, by arm, will be presented. In addition, acceptability between the active and placebo arms will be compared using the t-test or Mann-Whitney U test depending on the distribution of the data.

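### The secondary acceptability comparison uses one unadjusted exit rating; adjusting for site and an Enrollment acceptability score would be a cheap, modest gain in precision

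*SAP*

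**What the plan says.** Protocol 10.4.2 defines the endpoint, with 91 days as the period of use: "Overall acceptability will be measured by the degree (on a scale of 1 to 10) to which participants like or dislike using the IVR". SAP 9.2 takes it from question J2, an overall-liking item scored 1 to 10 and answered at the Product Use End Visit (PUEV) or the Early Termination Visit. The comparison is that "acceptability between the active and placebo arms will be compared using the t-test or Mann-Whitney U test depending on the distribution of the data". SAP 3.1 defines the analysis set as "all participants who completed question J2 of the product use end visit computer assisted self-interview (PUEV CASI) behavioral questionnaire".

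The exit visit is not the only time the topic is covered. Protocol 7.9 says that "A product preference/acceptability questionnaire will be administered by CASI to participants at the Enrollment Visit and Visit 6 (Day 28"), with a fuller questionnaire at exit. The Appendix I row "Collect product preference/acceptability information" is marked at Enrollment, Day 28 and Day 91. Arm assignment is stratified by site (Protocol 10.6, SAP 2.3). SAP 5 lists linear regression among the methods for continuous outcomes, but SAP 9.2 does not call on it. No SAP section names a use for the Enrollment or Day 28 acceptability answers.

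**The concern.** The comparison has 48 women, split 2:1. When a pre-treatment measure related to the outcome is already in hand, adjusting for it removes residual variance at almost no cost. Adjusting for the stratification factor also brings the analysis into line with the randomisation. SAP 9.2 does neither. A completers-only set also leaves out a woman who answered the Day 28 questionnaire but gave no exit rating. At stake is the width of the confidence interval for the difference in liking between the active and placebo rings.

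**Working it through.** **Inputs.** From Protocol 10.4.2: "the standard deviation of this score is approximately 2.4", "32 participants in the active IVR arm and 16 in the placebo arm", and the claim that "the study will have 90% power to detect a difference in the acceptability score of 2.65". From SAP 5: two-sided 5%. From Protocol 10.5: a retention target of 95%. The correlation ρ between an Enrollment score and exit J2 is in neither document, so it is assumed over a range.

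**Step 1: the plan's own figure.** The standard error of the difference is 2.4 × √(1/32 + 1/16) = 0.735. By the noncentral t with 46 degrees of freedom, power at 2.65 is 0.942 and the difference detectable at 90% power is 2.43. The normal approximation gives 0.950 and (1.960 + 1.282) × 0.735 = 2.38. The stated 2.65 is therefore not reproduced. A t-test on 85% of the sample would give it, but the protocol states no such allowance. The figure is conservative for the planned t-test, so the baseline used below is 2.43.

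**Step 2: adjusting for an Enrollment score.** The residual SD becomes 2.4 × √(1 − ρ²), with arm sizes and alpha unchanged:

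| Assumed ρ | Residual SD | Detectable at 90% power | Reduction | Power at 2.0 points |
|---|---|---|---|---|
| 0 | 2.400 | 2.43 | – | 0.76 |
| 0.1 | 2.388 | 2.42 | 0.5% | 0.76 |
| 0.3 | 2.289 | 2.32 | 4.6% | 0.80 |
| 0.5 | 2.078 | 2.11 | 13.4% | 0.87 |

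The 2.0-point column is a chosen illustration and not a protocol target.

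**Step 3: degrees of freedom spent.** SAP 2.1 names three sites, so site uses 2 degrees of freedom and the score 1, leaving 46 − 3 = 43. Repeating step 2 with 43 gives 2.437, 2.425, 2.325 and 2.111, against 2.433, 2.421, 2.321 and 2.107 with 46. The cost is about 0.004 points. Any gain from the site term itself cannot be sized, because the documents give no between-site variation in liking.

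**Step 4: missing exit ratings.** At the retention target, 48 × 0.05 = 2.4, so about 2 to 3 women would lack a rating. Complete-case analysis then moves the detectable difference from 2.43 to 2.50, and power at 2.65 from 0.942 to 0.930. At 90% retention the figures are 2.57 and 0.916. If a Day 28 rating of the same item were available for everyone, a likelihood model would multiply the detectable difference at exit by √(1 − ρ²f), where f is the fraction missing and ρ is now the Day 28 to exit correlation. For f = 0.05 this is √0.9955 = 0.998 at ρ = 0.3 and √0.9755 = 0.988 at ρ = 0.7, a gain of 0.2% to 1.2%. For f = 0.10 the gain is 0.5% to 2.5%.

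**The case against.** The case for leaving the plan alone is strong on four counts.

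- An unadjusted comparison of a randomised exit rating is valid, and by the protocol's own yardstick it is not short of power: about 94% at 2.65.
- Most early leavers are covered. J2 at an Early Termination Visit counts (SAP 9.2). Women whose product is stopped by a clinician for reasons other than HIV infection or pregnancy are asked to complete the Visit 9 procedures if willing (Protocol 7.5.3). Sites also try to obtain a final evaluation from anyone who withdraws (Protocol 9.9).
- SAP 5 promises secondary analyses for any missing data, and SAP 3.2 and 5 add imputation-based sensitivity analyses above 10% missing.
- Neither document shows that an overall-liking item is asked before exit. An Enrollment answer precedes ring use, so it can reflect only expectation or preference.

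All four stand, with one qualification. The missing-data text is generic, and because the set is defined as J2 completers, the SAP does not say which denominator the 10% trigger uses for this endpoint.

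A reader might infer that power is definitely lost, or that women who dislike the ring are dropped and the exit mean is biased upward. The documents support neither. The first needs a correlation that they do not give. The second needs women who leave without an exit visit, in numbers and with ratings that the documents do not indicate; bias in the arm comparison would further require the losses to affect the two arms differently.

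**Conclusion.** The point holds as a modest, near-costless improvement to a secondary endpoint. It does not correct an error, and no bias is shown. With SD 2.4, 32 against 16 and two-sided 5%, the difference detectable at 90% power goes from 2.43 to 2.42, 2.32 or 2.11 for an assumed Enrollment-to-exit correlation of 0.1, 0.3 or 0.5. At 0.3 or below the reduction is under 5%, and a low value is plausible. Day 28 data would add little to the exit comparison at the targeted retention. Whether they can be used at all depends on questionnaire content that is not in the documents.

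**What to change.** In SAP 9.2, make the main between-arm result the difference in PUEV/Early Termination J2 with its 95% CI, from a linear regression on arm, site and a named Enrollment acceptability score. Keep the Mann-Whitney test as a sensitivity analysis.

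If the Day 28 CASI carries the overall-liking item, add a supportive repeated-measures model including every woman with at least one on-ring rating. Day 28 should enter as an outcome and not as a covariate, because it is measured after randomisation and may itself be affected by arm. The exit difference should stay the reported result, since averaging the two visits would change the endpoint. If the item is not asked at Day 28, say so and omit this model.

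The cost is a few sentences of SAP text and one model on data already scheduled for collection. The downsides are three degrees of freedom for the main model and reliance on a parametric model for a 10-point scale, which the retained Mann-Whitney test helps to check.

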3.2 Statistical Analysis Issues

Based on previous MTN trials, minimal missing data is expected for the primary PK and safety endpoints. Any missing data will be tabulated as a separate category when reporting data summaries.

If missing data rates are higher than anticipated (over 10%), secondary sensitivity analyses will be conducted to assess the impact of the missing data on the study endpoints. These analyses will include imputing the data under the most extreme scenarios of information missingness, such as assuming everyone missing has an extreme value of the missing variable, and less informative imputation approaches.

4. INTERIM ANALYSIS AND DATA MONITORING COMMITTEE

No interim statistical analysis was planned or performed for the MTN-038 study.

One study monitoring committee (SMC) review was conducted for MTN-038 with a report date of May 17, 2019. Evaluation of safety was based on descriptive tables of adverse events, with no formal statistical testing.

5. GENERAL ANALYSIS METHODS

Descriptive statistics will be used to assess group characteristics or difference by study arm. Continuous variables will be summarized using the number of non-missing values, mean, standard deviation, median, interquartile range (IQR), and range (minimum and maximum). Categorical variables will be summarized using the number of missing values, frequencies, and percentages. The Pearson-Clopper method¹ will be used to obtain 95% confidence intervals on the proportion of binary variables where applicable.

Within-treatment group assessment of the change from the baseline measurement to a follow-up measurement will be analyzed using McNemar's test (for categorical response variables) or the paired t-test or Wilcoxon signed-ranks test (for continuous variables).

When use of formal testing to assess differences between arms is required, the following methods will be used: Fisher's exact test or logistic linear regression for categorical response variables; t-test or linear regression for continuous outcomes. Hypothesis tests for the primary and secondary endpoints comparing the two study arms (active and placebo IVR arms) will have a two-sided significance level of 5%.

To assess the adequacy of the randomization, participants in each of the two arms will be compared for baseline characteristics including demographics and laboratory measurements using descriptive statistics. Due to the small sample size, formal comparisons will not be done.

In any situation with missing data, appropriate secondary analyses will be performed to adjust for variables that may be related to the missingness mechanism. If missing data rates are higher than 10%, covariates that are related to missingness in likelihood-based regression models will be included. A sensitivity analysis to assess the potential impact of the missing data will also be performed. These analyses will include imputing the data under the most extreme scenarios of information missingness,

such as assuming everyone missing has an extreme value of the missing variable, and less informative imputation approaches.

6. TRIAL PARTICIPANT DISPOSITION

6.1 Disposition of Participants

Enrollment of participants took place at three study sites in the U.S: San Francisco, CA, Pittsburgh, PA, and Birmingham, AL. The participants screened and the reasons for those not enrolled will be summarized in a table by study site. The participants screened and enrolled by month will be summarized by study site. In addition, a consort diagram will describe the screening, eligibility, enrollment, randomization, and follow-up for the participants in this study.

6.2 Retention

For each visit, a participant is expected to have returned to the site clinic within a protocol-specified visit window based on the date of her enrollment visit. The proportion of participants retained at a scheduled visit is obtained by dividing the number of participants who have completed the visit by the number of participants expected for that visit. Tables will be presented that show by visit the number and percentage of expected, retained, and missed visits in addition to participants lost-to-follow-up or terminated early from the study by site and by arm. No formal statistical testing will be conducted.

6.3 Study and Study Product Discontinuation

The number and percentage of participants who completed the study, along with the number and percentages of participants who did not complete the study for the reasons collected on the Study Termination eCRF will be presented in tables by site and by arm. Reasons for not completing the study include the following: death, participant refusal of further participation, unwilling to comply with study procedures, lost to follow-up, investigator decision, participant refusal of further study product use, unable to contact participant, early study closure, pregnancy, HIV infection, adverse event, protocol deviation, allergic reaction to IVR, breastfeeding, non-therapeutic drug use, and other. No formal statistical testing will be conducted.

The number and percentage of participants who completed the study product regimen, along with the number and percentages of participants who did not complete the study product as specified per protocol for the reasons collected on the Discontinuation of Study Product eCRF will be presented in tables by site and by arm. Reasons for not completing the study product regimen per protocol include the following: death, participant refusal of further participation, unwilling to comply with study procedures, lost to follow-up, investigator decision, participant refusal of further study product use, unable to contact participant, early study closure, study terminated by sponsor, withdrawal of consent by participant, pregnancy, HIV infection, one or more reactive HIV test results or acute HIV infection suspected, adverse event, protocol deviation, allergic reaction to IVR, breastfeeding, non-therapeutic drug use, reported use of PEP, reported use of PrEP, use of anticoagulant, and other. No formal statistical testing will be conducted.

6.4 Visit Adherence: Completion of procedures

Completion of the following required and expected procedures will be evaluated: 1) physical exams; 2) vital signs; 3) pelvic exams; 4) pregnancy tests; 5) HIV tests; 6) plasma archive; 7) chemistries; 8) CBC with differential and platelets; 9) creatinine; 10) plasma for PK; 11) vaginal swabs for microbiota; 12) vaginal gram stain; 13) cervicovaginal fluid for anti-HSV-2 activity; 14) cervicovaginal fluid for PK; 15) cervicovaginal fluid for biomarkers; 16) cervicovaginal lavage for PK, PD or biomarkers; 17) cervical biopsy for PK; 18) cervical biopsy for PD; 19) rectal fluid for PK; 20) returned IVRs; 21) behavioral assessment; 22) In-depth interview. Tables displaying the number and percentages of participant-visits in

which these procedures were completed, by arm and by site, will be presented. No formal statistical testing will be conducted.

6.5 Protocol Deviations

Protocol deviations, as collected in the protocol deviations log eCRF will be reported. The number and percentage of participants with protocol deviations, along with the number and percentage of participants experiencing each type of protocol deviation, will be tabulated by site and by arm. Type of deviations include: inappropriate enrollment, failure to follow randomization or blinding procedures, study product management deviation, study product dispensing error, study product use/non-use deviation, study product sharing, study product not returned, conduct of non-protocol procedure, improper AE/EAE follow-up, unreported AE, unreported EAE, breach of confidentiality, physical assessment deviation, lab assessment deviation, mishandled lab specimen, staff performing duties that they are not qualified to perform, questionnaire administration deviation, counseling deviation, use of non-IRB/EC-approved materials, use of excluded concomitant medications, devices, or non-study products, informed consent process deviation, visit completed outside of window, other.

Additionally, a listing with all the recorded protocol deviations will be presented, including the description of the deviation, the steps taken to address the deviation and the steps taken to prevent future occurrences.

7. BASELINE DATA

Baseline characteristics of all enrolled participants will be compared by their treatment assignment as randomized and by site. No formal statistical comparisons will be performed for any of the baseline results below.

7.1 Demographics

Baseline demographic characteristics will include race/ethnicity, age and age category, sex at birth, gender identity, and gender of sex partners. Summary statistics appropriate for the measurement scale will be presented in tables by site and by arm.

7.2 Baseline Medical History

The number and percentage of participants reporting a medical history, as collected on the Medical History CRF, will be tabulated by site and by arm. A listing of all the medical history events will be presented, including whether the event is gradable, severity (if applicable), whether the condition is ongoing, and the beginning and end dates of the events.

7.3 Vital Signs

Baseline vital signs as collected on the Vital Signs eCRF at Screening and Enrollment will be presented for each visit, by arm and by site. Summary statistics appropriate for continuous outcomes will be used to describe distribution of height (at Screening only), weight, body temperature, systolic blood pressure, diastolic blood pressure, pulse, and rate of respiration.

7.4 Physical Exam

Baseline physical exam results as collected on the Physical Exam eCRF at Screening and Enrollment will be presented for each visit in tables by arm and by site. Number and percentage of participants experiencing any abnormal physical findings at each visit will be presented as well as the number and proportions of participants with findings for the following organ systems and body parts: general appearance; head, eye, ear, nose, and throat; neck; lymph nodes; heart/cardiovascular; lung/respiratory; abdomen; extremities; neurological; skin; and other system.

7.5 Pelvic Exam

Baseline results from the pelvic exam as collected on the Pelvic Exam eCRF at Screening and Enrollment will be presented in tables by arm and by site. Number and percentage of participant-visits for which any abnormal finding was reported will be presented, as well as the number and percentage of specific types of pelvic exam findings.

